| Intervention(s) | 
Study arm 1: Treatment
 
 Participants assigned to this group will receive an automated bidet (TOTO Washlet S300e with remote control) and an occupational therapy intervention over 2-3 in-home visits. During the first intervention visit, a licensed contractor will install the bidets in participants' homes. The OT will then educate and train the caregiver and care recipient to successfully use the bidet, and make any modifications to the remote as needed. Throughout the intervention, the OT will use motivational enhancement strategies. The OT will make minor modifications to the remote as needed. A second intervention visit will occur 1-2 weeks post-installation to address any new difficulties. Check-in phone calls will be offered to the caregiver and care recipient if needed. 
Study arm 2: Waitlist Control
 
 Caregivers will wait for 30 days and then will be offered the intervention. No intervention. |
| Key Inclusion and Exclusion Criteria | 
Inclusion criteria:
 
(1) provided unpaid care and lived with a care recipient aged 55 years or older
 
(2) assisted with toileting for at least 6 months
 
(3) did not have an automated bidet
 
(4) had a working toilet and bathroom outlet, and (5) their care recipient was willing to participate
 
Exclusion criteria:
 
(1) Caregivers scoring 10 or above on the Short Blessed Test, indicating possible cognitive impairment
 |
| Study Type | Randomized waitlist control feasibility study |
| Date of First Enrollment | December 20, 2016 |
| Target Sample Size | 10 |
| Recruitment Status | Complete |
| Primary Outcome(s) | 
 Number of participants recruited Number of caregivers retained Ability to install the automated bidets, including any modifications needed Caregivers' or care recipients' ability to operate the bidet Acceptability Preliminary efficacy: reduction of physical barriers to toileting Preliminary efficacy: Performance Preliminary efficacy: Satisfaction Preliminary efficacy: Self-efficacy Adverse events |

Organizational Structure and Responsibilities

[name]., OTR/L FAOTA is the principal investigator and will manage and oversee all aspects of this project. She will ensure compliance with quality-assurance requirements as stipulated by human subjects, and submit appropriate materials as needed throughout the study.

[name], OTD/S will coordinate this study by developing study materials, reporting adverse and serious events for all participants, recruiting, screening, and enrolling participants, as well as implementing quality control procedures, and assisting in data management and analysis. She will also develop materials for regulating bodies with assistance from study staff.

[name], MS, OTR/L will supervise and train staff during this study.

[name], OTD, MSCI, OTR/L will train staff and assist with assessments and statistical analysis performed for this project.

[name], MS will assist with data analysis for this study and maintain randomization codes.

Study Objectives

The objective of this feasibility study is to assess the acceptability and preliminary efficacy of a toileting intervention using an automated bidet system and training by an occupational therapy practitioner (OT) to reduce the amount of physical assistance required from caregivers.

Background & Study Rationale

[figure not shown]
Informal caregivers are unpaid family members or friends that provide over 30 billion hours of care annually for older adults (Chari, Engberg, Ray, & Mehrotra, 2015). They assist with activities of daily living (ADLs) and instrumental activities of daily living (IADLs), enabling their loved one to remain at home (Darragh et al., 2015; National Alliance for Caregiving and AARP Public Policy Institute, 2015). However, they often receive little to no training, especially for assisting with toileting, and are at an increased risk for physical injury, stress, and burnout (Darragh et al., 2015; National Alliance for Caregiving and AARP Public Policy Institute, 2015). This jeopardizes their loved ones' ability to age in place. Care recipients are more likely to be placed in a nursing home if they have difficulties completing ADLs such as toileting (Luppa et al., 2010).

Informal caregivers report that assisting with toileting and managing incontinence are some of the most difficult ADLs (Darragh et al., 2015; King, Holliday, & Andrews, 2018; National Alliance for Caregiving and AARP Public Policy Institute, 2015). Informal caregivers with low self-efficacy or beliefs about their ability to assist with toileting tasks are at risk of experiencing depression or burnout (Bandura, 1982; Gilliam & Steffen, 2006; Grano, Lucidi, & Violani, 2017). Thus, a potential solution is an automated bidet system, a toilet seat with built-in cleaning features, to replace physical support provided by a caregiver for toileting. Automated bidet systems have been shown to reduce caregivers' use of non-neutral postures by 15% and severe trunk flexion by 32% (King et al., 2019). In another study, participants reported an increase in competence, adaptability, and self-esteem after using an automated bidet system compared to their regular toileting routine (Yachnin, Gharib, Jutai, & Finestone, 2017). Automated bidet systems have the potential to increase caregivers' self-efficacy, increase caregivers' satisfaction, reduce the amount of physical assistance needed for toileting, and decrease caregivers' risk for injury when assisting with toileting.

Study Design

In this randomized waitlist control feasibility study, ten informal caregivers and care recipient dyads will be recruited to the study and randomly assigned to either the treatment group or the waitlist control group. The treatment group will participate in the intervention immediately, receiving the automated bidet system and training, while the control group waits to receive the automated bidet. After completion of this phase, control participants will be provided with the automated bidet system and subsequent training. Outcome measures will be collected at pretest and posttest (30 days post-intervention for the treatment group or 30 days post-enrollment for the control group), and at follow-up for the waitlist control group (30 days post-installation). Assessments will be used to evaluate the feasibility of the feasibility, acceptability, and preliminary efficacy of this OT intervention to reduce the amount of assistance needed from caregivers. Overview of the study's major steps is shown in Figure 1.

Figure 1: Study Flow Diagram

Participants

Ten informal caregivers will be recruited to participate in this study from a study registry, clinicians, exercise groups, and word of mouth in St. Louis, Missouri.

Informal caregivers will be contacted by phone and screened for eligibility. Caregivers will be eligible for this study if they: (1) provide unpaid care and lived with a care recipient aged 55

years or older; (2) have assisted with toileting for at least 6 months; (3) do not have an automated bidet; (4) have a working toilet and bathroom outlet; and (5) their care recipient is willing to participate. Participants will be excluded if they score a 10 or above on the Short Blessed Test, indicating a possible cognitive impairment.

Informed Consent

Written informed consent to participate in the study will be obtained before any assessments are conducted. If eligible, an occupational therapist (OT) will schedule a time to obtain consent at the potential participant's home. All elements of consent will be reviewed with caregivers prior to enrolling in the study, including the purpose of the study, risks, benefits, alternatives to the study, how confidentiality will be maintained, the PI's contact information, no consequences to withdrawal, and how study results will be shared. Participants will be given a copy of the signed consent for their records.

A written waiver of consent/exempt information sheet will be presented in person to all care recipients at the initial interview prior to administering the IHOPE-Assist. The OT will review the exempt information sheet with the care recipient during the consent visit in a private setting, including the purpose of the study, study procedures, and how confidentiality will be maintained. If the care recipient does not want to participate in the performance-based component of the evaluation, which includes toileting activities normally done in the home with the assistance of a caregiver, then the caregiver and care recipient will not be enrolled in the research study.

All study staff have undergone IRB training. In addition, all staff members have participated in cultural competence training and are trained to interview older adults. All study documents will be available in multiple formats, are developed in 12-point Arial font, and are written in plain language. If a participant needs to be re-consented at any point during the study, the study staff will visit the person in home and repeat the consent process. All signed consents will be stored in the office of the PI under double locks.

Study Intervention

After randomization, the OT will contact all participants to inform them of their group allocation (Treatment or Control). A home visit will be scheduled as soon as possible for the participants in the treatment group. The waitlist control group will wait 30 days before receiving the automated bidet system and subsequent training.

Intervention Procedures. A visit will be scheduled after the pretest visit for installation and training on the automated bidet system (TOTO Washlet S300e with remote control). During the first intervention visit, the licensed contractor will install the automated bidet. After installation, the OT will provide training to the caregiver and care recipient on using the automated bidet system and will make modifications to the remote as needed. A second intervention visit will be completed 1-2 weeks post-installation to address any new difficulties with using the automated bidet system. During the intervention visits, the OT will utilize motivational enhancement and active practice, and provide education on programming the remote control for the care recipient's desired temperature, water pressure, and wand position to increase independence with toilet hygiene. The caregiver will be instructed to contact the OT if they have any questions.

Control Group Procedures. The procedures for the waitlist control group will be the same as above. During the initial 30 days, participants randomized to the control group will wait to receive the automated bidet. After completing assessments after the first 30 days, they will receive the automated bidet and follow the same intervention procedures described above.

Randomization

Caregivers will be randomized using a 1:1 ratio by gender with a web-based randomization tool, Research Electronic Data Capture system (REDCap) after signing the consent (Harris et al., 2009). Randomization sequence concealment will be achieved by the Research Electronic Data Capture (REDCap) system (Harris et al., 2009).

Data Collection

Data will be collected at pretest and posttest (30 days post-intervention for the treatment group or 30 days post-enrollment for the control group), for the caregiver and care recipient in the participants' homes. Caregivers in the waitlist control group will also complete assessments at follow-up (30 days post-installation).

Covariate Assessments to be collected during the initial screening from the caregiver:

Demographics. Caregivers will be asked basic demographic information that includes birthdate, gender, marital status, ethnicity, income, years of education, years of caregiving, relation to care recipient, diagnosis of care recipient, and hours of caregiving provided per week.

Short Blessed Test (SBT). The SBT is a six-item measure that will be used to assess the caregiver's cognition, memory, and orientation as a screening tool prior to enrolling in the study (Katzman et al., 1983). The SBT has good validity. The score for each item is calculated based on the number of errors and a weighting factor; these scores are combined to calculate the total score. Total scores range from 0-28; higher scores indicate more cognitive impairment. Informal caregivers who score 10 or above will not be eligible for the study as that indicates impairments consistent with dementia.

Primary endpoint assessments to be completed by the caregiver throughout the study:

In-Home Occupational Performance Evaluation for Providing Assistance (I-HOPE Assist). The I-HOPE Assist is a reliable and valid assessment which measures caregivers' self-reported satisfaction and performance, impact of environmental barriers, and self-efficacy for assistance with 43 specific daily activities (Keglovits, Somerville, & Stark, 2015). Caregivers use activity cards to identify the top 10 caregiving activities which are difficult or worrisome for them, one of which must be toileting. Next, they provide self-ratings of their performance, satisfaction with performance and self-efficacy for those activities on a scale of 0 to 5, with higher scores indicating better performance, satisfaction, and self-efficacy. For self-care and transfers for toileting, the OT will also record barriers to performance and rate the impact of the barrier on the caregiver's performance, yielding scores of barrier severity. This assessment will be used to measure changes in caregiver performance, satisfaction, and self-efficacy for providing assistance with toileting to evaluate the effects of the automated bidet system intervention on caregiver outcomes.

Process Evaluation. During the final study visit, caregivers will complete an 8-item process evaluation to assess the feasibility of the toileting intervention using an automated bidet system. Caregivers will rate how much they thought the automated bidet: (1) made assisting with toileting easier, (2) improved their confidence, and (3) addressed their concerns for assisting the care recipient with toileting. Caregivers will rate agreement with statements about the appearance, ease of use, and training and whether they will continue to use the automated bidet after the study on a scale of 0 (strongly disagree) to 4 (strongly agree), with higher scores indicating greater acceptance of the intervention. Caregivers will also complete a qualitative

interview to determine whether the number and length of visits were sufficient.

Statistical Analyses

Descriptive statistics will be used to examine demographic characteristics and feasibility outcomes. A Wilcoxon-signed rank test will be used to examine secondary outcomes to compare groups. Qualitative interviews will be analyzed using a grounded theory approach and constant comparative analysis.

Potential Benefits, Risks, and Alternatives

Benefits. Participants may or may not benefit from being in this study. The information from this study may help researchers to better understand and address the needs of caregivers in the future.

Risks. Visits may result in feeling tired or disrupted. In addition, some questions, or demonstrations performing activities caregivers assist with, may touch on emotionally sensitive issues that could cause anxiety, embarrassment, or other forms of emotional stress.

Participants will be told that their involvement in this research study is voluntary and that they may choose not to participate or to withdraw their consent at any time. Participants who undergo the study visits will be given the option to take a break or reschedule the visit at any time. All research-related information will be kept confidential and accessible only to authorized members of the research team.

Minimization of Risks and Confidentiality

To protect against and minimize potential risks, participants will be carefully screened and evaluated for eligibility by the research coordinator. To avoid or minimize symptoms of fatigue or emotional distress during visits, participants will be instructed to notify the rater or interventionist if they experience any discomfort. They will also be periodically questioned about their tolerance for the tests/intervention. Testing and interviews will be terminated if participants develop fatigue or emotional distress.

To help protect participants' confidentiality, an ID number will be assigned to each participant. All data collected from a participant will be labeled with that ID number. All participant electronic and hard-copy data will be kept under double-lock protection. All hard-copy forms that contain personal identifiers (e.g., name, address, phone number) will be stored in a separate, locked file drawer under double-lock protection. No publication or presentation of the study data will uniquely identify or provide sufficient information to uniquely identify participants.

To guard against unauthorized data access, all shared-use computer systems at Washington University School of Medicine are protected with passwords, which are changed at 4-month intervals. Only individuals with a particular "need to know" status are given access, and system privileges are carefully restricted. All personal computers to be used in the Administrative Unit are located within a secure area, and the system is locked when not in use. SAS and SPSS software packages will be used for data management and analysis. Datasets generated from these programs will be password protected, which will make accessing study data difficult even in the event that unauthorized computer access occurs.

Adverse Event Reporting and Safety Monitoring

All SAEs will be reported to the Human Research Protection Office in the following time frames: (a) death—immediately, (b) life-threatening—within 7 calendar days, (c) all other SAEs—within 15

calendar days using the Electronic Serious Adverse Event Reporting System. Should an SAE occur that increases the risk to the participants, the study will be stopped, an investigation will be conducted, and a findings report will be generated before the study is resumed.

[name] will be responsible for reviewing study progress and outcomes including recruitment, data quality, safety, and efficacy. Quarterly reports will be reviewed by the principal investigator. Because risk in the proposed study is considered minimal, the data monitoring plan will include continuous, close monitoring by the study investigator with prompt reporting of any AEs. [name] will monitor the study for AEs, adherence to the protocol, and safety.

Premature Study Termination

Preliminary study data will be monitored by the data management team for any potentially harmful outcomes. If interim data raise significant safety concerns, the trial will be ended early.

Indemnity

Washington University School of Medicine is responsible for any non-negligent damage incurred as a result of participating in this study. The indemnity is renewed on an annual basis. Washington University School of Medicine assures that it will continue renewal of the indemnity for the duration of the trial.

Ethics and Dissemination

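### The randomised posttest is timed from a different event in each arm, so it tends to fall later in the treatment arm and elapsed time differs in any between-arm comparison (minor)

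*Combined protocol and SAP*

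**What the plan says.** All references are to the combined protocol and SAP.

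- **Posttest timing.** Study Design and Data Collection both give the schedule as "pretest and posttest (30 days post-intervention for the treatment group or 30 days post-enrollment for the control group".
- **Control follow-up.** This uses a third clock: "Caregivers in the waitlist control group will also complete assessments at follow-up (30 days post-installation".
- **Start of treatment.** Study Design says "The treatment group will participate in the intervention immediately". Study Intervention gives the steps: "After randomization, the OT will contact all participants to inform them of their group allocation (Treatment or Control", and a home visit is then arranged as soon as it can be. Under Intervention Procedures, installation and training take place at a visit after the pretest visit, and a second intervention visit comes one to two weeks after installation.
- **Extent of the intervention.** The front table, Intervention(s) row, describes "an occupational therapy intervention over 2-3 in-home visits".
- **Control wait.** The same row says "Caregivers will wait for 30 days and then will be offered the intervention". Study Intervention and Control Group Procedures also state a 30-day wait, with control assessments done before the bidet is supplied.
- **Analysis.** Statistical Analyses names a Wilcoxon signed-rank test for comparing groups. It describes no adjustment for elapsed time.

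The available text gives no visit window and does not say which event ends the intervention. Study Design refers the reader to a flow diagram ("major steps is shown in Figure 1"), which is not reproduced in the text available to this review and may say.

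**The concern.** A concurrent waitlist arm is there to absorb change that would have happened anyway. It does that fully only if both arms are observed over the same elapsed time. Here the control clock starts at enrollment and the treatment clock starts at a later event. Any change over time in I-HOPE Assist ratings during the extra days is counted as part of the difference between arms. Randomisation balances the dyads but not the assessment schedule.

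The outcomes at stake are barriers, performance, satisfaction and self-efficacy, which the front table lists among the primary outcomes under preliminary efficacy. Retention is touched as well, since the arm observed for longer has more time in which to lose dyads.

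**Working it through.** **Inputs**

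- Control posttest: day 30 from enrollment (Study Design, Data Collection).
- Treatment posttest: 30 days post-intervention (same sections).
- *V*, days from installation to the end of the intervention. Reading A: the intervention ends at the second visit, so *V* = 7 to 14 (Intervention Procedures). Reading B: post-intervention means post-installation, so *V* = 0.
- *L*, days from enrollment to installation. It is not stated; I assume 0 to 14.
- Day 0 is enrollment, taken to be the randomisation day (assumption). A possible third visit is left out because its timing is not given.

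Both readings are tenable. The description of an intervention spread over several visits favours A. Dating the control follow-up from installation, after the same procedures, favours B.

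**Timing**

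Treatment posttest day = *L* + *V* + 30. Gap between arms = (*L* + *V* + 30) − 30 = *L* + *V*.

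| *L* (assumed) | B: posttest day | B: gap | A: posttest day | A: gap |
|---|---|---|---|---|
| 0 | 30 | 0 | 37-44 | 7-14 |
| 3 | 33 | 3 | 40-47 | 10-17 |
| 7 | 37 | 7 | 44-51 | 14-21 |
| 14 | 44 | 14 | 51-58 | 21-28 |

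The gap is never negative. It is zero only under B with installation on the enrollment day, which is unlikely given that the dyad is contacted after randomisation and a contractor visit is then arranged. Under A at *L* = 0 the gap is 7/30 = 23% to 14/30 = 47% of the control interval. The date of the pretest does not alter the gap, provided it is held at the same point in both arms.

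**How much drift would matter (illustration)**

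Assume five dyads per arm (1:1 allocation met exactly) and an SD of change of 1.0 on the 0-5 scale, with a range of 0.5 to 1.5. The documents give no SD.

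SE of the between-arm difference = SD × √(2/5): 0.32 at SD 0.5, 0.63 at SD 1.0, 0.95 at SD 1.5.

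Drift per 30 days that would move the difference by half an SE = 0.5 × SE × 30 / gap:

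| SD | gap 7 days | gap 14 days |
|---|---|---|
| 0.5 | 0.68 | 0.34 |
| 1.0 | 1.36 | 0.68 |
| 1.5 | 2.03 | 1.02 |

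At SD 1.0, untreated ratings would have to move by 0.68 to 1.36 points a month on a five-point range. Nothing in the documents suggests drift of that size.

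**The case against.** The strongest case against is materiality. This is a ten-dyad feasibility study with efficacy labelled preliminary, and the drift needed to shift the comparison noticeably is large. Participants requires that caregivers "have assisted with toileting for at least 6 months", so rapid adaptation during an extra week or two is unlikely. This stands, and it is why the point is minor.

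The size of the gap is also only partly documented. The 7-14 days depends on Reading A. Under B the gap is *L*, and the stated intention to start at once suggests that *L* is short. This stands too. Figure 1 may choose between the readings, so the lack of a definition should not be called an omission. Choosing a reading would not by itself make the two stated starting events the same.

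The named test is paired. If it is run within dyads, pretest to posttest, the difference between arms in calendar time does not enter it. That is correct. The concern applies to a comparison between arms, which the stated aim of comparing groups implies but the named test does not itself perform.

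A reader might go further and infer that the schedule favours the bidet, or that the 23-47% measures bias. The documents support neither. The direction of any drift is unknown, and a share of a calendar interval says nothing about how far ratings move. It would equally be unsupported to say that retention is untouched, because observation time differs by arm.

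**Conclusion.** The point holds as a minor one. As written, the treatment posttest tends to fall later than the control posttest: by at least 7-14 days if the intervention ends at the second visit, otherwise by the unstated installation lag. The order follows from the plan's own sequence of visits. The amount rests on the reading of post-intervention, on *L*, and on enrollment being the randomisation day.

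The consequence is an avoidable time difference in any between-arm comparison of I-HOPE Assist change, probably small beside sampling error and of unknown sign. It does not invalidate the study.

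A side effect appears under Reading A. Treated dyads are assessed 37-44 days after installation, and control dyads 30 days after installation at their follow-up, so those two assessments would not match in exposure either.

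**What to change.** **For a schedule still open.** Time the posttest in both arms from randomisation, with one common target day and window late enough to keep the planned treatment exposure. State which event post-intervention refers to, unless Figure 1 already does. The 30-day control wait and posttest appear in the front table, Study Design, Study Intervention (including Control Group Procedures) and Data Collection. These must be reconciled with the common timing. The length of the wait is for the investigators to decide.

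**Cost.** No visit is added. The control posttest, and what follows it, comes somewhat later. For scale, with *L* assumed at 1-7 days, treated dyads under the present plan fall on days 31-37 (B, midpoint 34) or 38-51 (A, midpoint 44.5), about 4 or 14.5 days after the control posttest. With *L* at 1-14 days the midpoints are 37.5 and 48, or 7.5 and 18 days after.

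A small residual gap can remain if installation does not run to plan and treated visits move to preserve exposure. For example, under A a day set for *L* of 1-7 would miss the treated midpoint for *L* of 1-14 by 48 − 44.5 = 3.5 days.

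**For visits already held** (the front table lists recruitment as complete). Report days from randomisation and from installation to each assessment, by arm, and qualify the between-arm efficacy comparison and the retention figures accordingly. This costs reporting effort only. It discloses the time difference but cannot remove it.

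### The plan gives no efficacy analysis for the waitlist arm's I-HOPE Assist scores after installation, and its one test is paired although the arms are independent

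*Combined protocol and SAP*

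**What the plan says.** Study Design states that "ten informal caregivers and care recipient dyads will be recruited to the study and randomly assigned" to immediate treatment or waitlist. Under Randomization, "Caregivers will be randomized using a 1:1 ratio by gender". No arm sizes are given, so the expected split is about five and five.

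Both arms are assessed at pretest and posttest, the posttest falling "30 days post-intervention for the treatment group or 30 days post-enrollment for the control group". The waitlist arm then crosses to the device: "After completing assessments after the first 30 days, they will receive the automated bidet and follow the same intervention procedures described above" (Control Group Procedures). It is assessed a third time. Study Design lists this visit, "at follow-up for the waitlist control group (30 days post-installation", and Data Collection repeats it: "Caregivers in the waitlist control group will also complete assessments at follow-up (30 days post-installation".

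The overview table lists barrier reduction, performance, satisfaction and self-efficacy as preliminary-efficacy outcomes. All four are measured with the I-HOPE Assist.

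The Statistical Analyses section has three sentences. One assigns descriptive statistics to demographics and feasibility outcomes, and one assigns a qualitative method to the interviews. The only inferential sentence is: "A Wilcoxon-signed rank test will be used to examine secondary outcomes to compare groups". It names no time points, no baseline and no pooling rule, and it does not mention the waitlist follow-up.

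**The concern.** By design every dyad is to be offered the bidet, and each should have an I-HOPE Assist assessment before installation and another about a month or more after it. For the waitlist half, the only scores recorded with the device in place come from the follow-up visit. If the analysis section is followed as written, those scores enter no efficacy analysis.

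The one named test adds to the uncertainty. A signed-rank test works on pairs, so it can compare two assessments of the same dyad but not two separate arms. A reader cannot tell whether a between-arm comparison, a before/after comparison in the treated arm, or a before/after comparison in all dyads is intended. The sentence also refers to secondary outcomes, while the overview table and Data Collection class the I-HOPE Assist measures as primary.

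Two things are at stake. One is precision in describing what happens to caregivers after installation, which a ten-dyad feasibility study can ill afford to lose. The other is analyst freedom: waitlist change could be taken from pretest or from the 30-day posttest, and pooled or not, after the scores have been seen.

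**Working it through.** The plan has no figure to reproduce. The sample size of 10 is a target given without alpha, power, effect size, standard deviation or dropout. The calculations below therefore measure only what the follow-up data would add.

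**Inputs from the documents:** 10 dyads; 1:1 allocation; waitlist arm exposed after its 30-day assessment; one waitlist assessment 30 days after installation.

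**Assumptions, not in the documents:** exactly 5 per arm, no dropout, no ties or zero changes, equal variance of change in both arms; for power, two-sided alpha 0.05 and normally distributed changes.

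**1. Share of exposed dyads.** 10 × 1/2 = 5 dyads are exposed only after the randomised comparison.

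**2. Standard error of the mean before/after change.** This is SD/√n. The ratio of n = 10 to n = 5 is √(5/10) = 0.71, a reduction of about 29%.

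**3. 95% interval half-width, in SDs of change.** This is t(0.975, n−1)/√n.
- n = 5: 1.24
- n = 10: 0.72

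**4. Smallest two-sided signed-rank p-value.** This is 2/2ⁿ.
- n = 5: 2/32 = 0.0625
- n = 10: 2/1024 = 0.002

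**5. The randomised contrast, for comparison.** With an exact rank-sum test, 5 against 5, the smallest two-sided p-value is 2/C(10,5) = 2/252 = 0.0079. The follow-up data do not alter this test or its precision.

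**6. Simulated power at assumed standardised changes.**

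| Standardised change | Signed-rank, n = 5 | Signed-rank, n = 10 | Rank-sum, 5 v 5 |
|---|---|---|---|
| 0.5 | 0 | 0.29 | 0.07 |
| 0.8 | 0 | 0.60 | 0.14 |
| 1.0 | 0 | 0.78 | 0.21 |
| 1.5 | 0 | 0.98 | 0.43 |

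The last two columns answer different questions. The n = 10 column is an uncontrolled change from baseline; the rank-sum column is a randomised difference.

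**7. Sensitivity to the split.** Randomisation by gender could give 4 and 6. The signed-rank floor in the treated arm would then be 2/16 = 0.125 or 2/64 = 0.031, and the rank-sum floor 2/C(10,4) = 2/210 = 0.0095. Ties on the 0 to 5 ratings would change all the exact p-values.

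**8. Timing.** The treatment posttest is counted from the intervention and the waitlist follow-up from installation, yet "A second intervention visit will be completed 1-2 weeks post-installation". If the intervention is taken to end at that visit (an assumption), treated dyads are assessed 30 + 7 = 37 to 30 + 14 = 44 days after installation, against 30 days in the waitlist arm.

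**The case against.** A reader might infer that the waitlist follow-up has no analysis at all. The documents do not support that. The process evaluation and qualitative interview take place at the final study visit, which for the waitlist arm is by schedule this follow-up, and both have a stated analysis. Only the I-HOPE Assist efficacy scores are left unassigned.

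A reader might also infer that half of the exposed dyads drop out of the efficacy estimate. That goes too far as well. In a between-group comparison all ten dyads contribute, the waitlist dyads as unexposed controls. The text neither states nor excludes a pooled before/after analysis.

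It can fairly be said that the 0.0625 floor belongs to a test in five treated dyads that the plan never specifies, judged against a 5% threshold that it never sets. That stands, and precision is therefore the better argument. Retention and uptake may also fall short of ten, since retention is itself an outcome and waitlist caregivers are only offered the device.

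The strongest objection concerns what the extra data can show. A before/after change is uncontrolled. Comparing change while waiting with change after installation does not separate device from time, because waiting always comes first: period, repeat assessment and regression to the mean stay confounded with the device. That contrast also has only about five dyads and the same 0.0625 floor.

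These points limit the claim and shape the remedy. They do not fill the gap: no method, baseline or pooling rule is given for these scores, and the named test does not suit independent arms.

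**Conclusion.** The concern holds in a limited form. The plan specifies no efficacy analysis for the post-installation I-HOPE Assist data of about 5 of the 10 dyads to be exposed, and its only inferential test is paired where the stated comparison is between independent arms. The loss is of exposed-state efficacy data, not of dyads.

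Under the 5/5, no-ties, no-dropout and equal-variance assumptions, using these data cuts the before/after standard error by about 29% and the interval half-width from 1.24 to 0.72 SD of change. Neither gain carries over to the randomised effect. This is a cheap improvement to a feasibility study; it does not invalidate the design.

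**What to change.** Replace the inferential sentence with three stated analyses.

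- **Controlled estimate.** Keep the randomised pretest-to-posttest comparison between arms, with an unpaired method such as an exact Wilcoxon rank-sum test on change scores.
- **Supportive estimate, labelled non-randomised.** In all exposed dyads, report a before/after signed-rank test with a Hodges-Lehmann estimate and confidence interval. Use pretest to posttest in the treatment arm and 30-day posttest to follow-up in the waitlist arm.
- **Descriptive only.** In the waitlist arm, show the waiting-period change beside the post-installation change, without claiming that this separates device effect from time.

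Before any pooling, reconcile the two timing anchors in Study Design with the second visit in Intervention Procedures, so that time since installation is defined in the same way in both arms.

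The cost is a few sentences, as the data are already scheduled. The downside is that the pooled estimate is uncontrolled and could be mistaken for the trial's main result if the label is lost. The overview table gives recruitment as complete; if results have already been seen, the added analyses should be labelled post hoc.
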